4.2 Planned Covariates

Covariates include, but are not limited to the following:

Stratification Factor

- atrial fibrillation/flutter per the interactive voice response system (IVRS stratification factor) (presence vs. absence)

Baseline Covariates

- age at study enrollment (< 65 vs. ≥ 65 years)
- sex (male vs. female)
- LVEF (< median vs. ≥ median)
- body mass index (BMI) (< median vs. ≥ median)
- NT-proBNP (< median vs. ≥ median)
- coronary artery disease (CAD) (presence vs. absence)

5. Hypotheses and/or Estimations

No formal hypothesis testing will be performed and all statistical approaches are hypothesis-generating. PK parameters following chronic dosing (BID for 16 weeks) will be estimated and presented along with confidence interval limits.

6. Definitions

6.1 Study Time Points

Randomization Date

The randomization date for each subject is the date the investigator (or designee) confirms in the IVRS that the subject has met all eligibility criteria and is randomized.

Enrollment Date

The enrollment date is the same as the randomization date. The enrollment date is a derived field on the electronic case report form (eCRF) page.

First Dose Date of Investigational Product (IP)

For each subject, the First Dose Date of Investigational Product is defined as the date of the first administration of IP as recorded on the IP administration eCRF page.

Study Day 1

The date of the first investigational product (IP) administration or the date of enrollment for subjects who were not administrated any dose of IP.

Study Day

For each subject and a given date of interest, study day is defined as the number of days since study day 1:

Study day = (date of interest – study day 1 date) + 1.

If the date of interest is prior to the study day 1:

Study day = (date of interest – study day 1 date).

Last Dose Date of Investigational Product

For each subject, the Last Dose Date of Investigational Product is defined as the date of the last administration of investigational product.

End of Study (EOS) Date

For each subject, the end of study date is the date recorded on the End of Study eCRF.

Study End Date

The study end date is the last end of study date of all randomized subjects.

6.2 Demographics and Baseline Related Definitions

Age

Age will be calculated as the subject's age in years at enrollment as recorded on the eCRF.

Baseline ECG

For ECG, the baseline value is defined as the mean over all non-missing triplicate averages of 3 (or all available) readings from each set of triplicate taken prior to or on Study Day 1.

Other Baseline Values

For all other variables, the baseline value is defined as the last non-missing value collected prior to or on Study Day 1.

Change from Baseline

The arithmetic difference between a post-baseline value and baseline for a given time point:

Change from baseline = (post-baseline value – baseline value).

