6.2.1.1 Dosage, Administration, and Schedule

Eligible outpatient subjects will be randomized and will initiate administration of IP (omeamtiv mecarbil or placebo). Day 1 is defined as the calendar day when treatment with IP is initiated. The first administration of IP should be on the day of randomization but not later than 5 calendar days after randomization. The time when ingestion of the first dose of IP is completed is defined as Time = 0 hours. Baseline procedures must be completed before initiation of IP and can be performed on the same day.

IP will be administered orally BID in the morning and evening by the subjects and can be taken under fasted or fed conditions. IP will be swallowed whole (not chewed) and taken with water as instructed in the IPIM. Administration of each morning and evening dose is to be taken at approximately the same time of day (12 ± 3 hours from the most recent previous dose). If IP cannot be taken or has not been taken within this window, the dose should be recorded as missed and the next dose should be taken at the regular time.

Administration of IP will start with the morning dose on day 1 and will end with the morning dose on the day of the subject's week 16 visit. The quantity, date and time, lot number, and bottle number of investigational product is to be recorded on each subject's eCRF.

6.2.1.2 Rules for Withholding Investigational Product due to Myocardial Ischemia or Infarction, Abnormal Blood Pressure or Heart Rate

Omecamtiv mecarbil may result in signs and symptoms of myocardial ischemia or infarction, as described in Section 7.1 of the Investigator's Brochure (eg, increases in HR, dizziness, dyspnea, hypotension, chest discomfort or pain, ST-segment depression on ECG, and/or elevations in troponin I or T). If a subject reports clinical signs or symptoms suggestive of myocardial ischemia or infarction, and/or experiences changes in BP or HR, withholding of IP should be considered. No antidote to omecamtiv mecarbil exists. Standard medical therapies should be used in the presence of signs or symptoms of myocardial ischemia.

The following are mandatory rules for withholding IP:

- The subject experiences clinical signs or symptoms, including ECG changes, consistent with myocardial ischemia or infarction as determined by the investigator
- The subject experiences a symptomatic decrease in systolic BP on 2 successive measurements

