^a If early discontinuation, week 20 (EOS) assessments should be performed as close as possible to time of discontinuation

^b Serious adverse events are collected from signing the informed consent until 30 days after the last dose of IP or EOS, whichever is later, adverse events and PEPs from randomization until EOS, recording of PEPs and hospitalization only during visits to the study site (day 1, weeks 2, 4, 8, 12, 16, 20 [EOS]); if subject is not seen at the study site, AEs/SAEs/PEPs can be collected by phone

^c Predose in the morning, at study site

^d Performed as close as possible after the collection of PK sample at 2 hours \pm 30 minutes following IP administration.

^e If cardiac troponin is measured locally to evaluate suspected myocardial ischemia or infarction, send samples for troponin I/CK-MB, and PK (up to 5 days after last dose of IP) to the central laboratory

^f Serum pregnancy testing in females of childbearing potential, FSH/LH or estradiol at screening only, and only if applicable per exclusion criteria.

^g IP is taken twice daily except on the last day of administration (week 16 visit). Subjects randomized to 37.5 mg BID target dose and 50 mg BID target dose will initiate administration at 25 mg BID. Subjects will be up-titrated to 37.5 mg BID or 50 mg BID target dose at the week 4 visit based on steady state $C_{predose}$ result from week 2. Subjects who do not have a week 2 PK value in time for dose adjustment at the week 4 visit, will be up-titrated at week 8 based on steady state $C_{predose}$ result from week 2, if available. Subjects will be up-titrated at the week 4 or week 8 visits only if the week 2 $C_{predose}$ is < 200 ng/mL. Otherwise, they will continue at 25 mg BID.

^h Details of IP dispensation and reconciliation are described in the IPIM; dispensation and reconciliation timepoints may differ from the timepoints shown above; IP not dispensed at week 16 visit.

ⁱ Paper Diary will be dispensed at Day 1 and will be collected at week 16. Subjects will be instructed to enter each administration of IP from Day 1 to week 16 or early termination. The date and time of administration will be noted.

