Qualitative or quantitative human chorionic gonadotropin pregnancy testing will be performed locally or per central laboratory, depending on investigator preference and to facilitate trial operations. Pregnancy testing is required as per Schedule of Assessments ([Section 7.1](#)) for all females of childbearing potential as defined in the exclusion criterion ([Section 4.1.2](#)).

7.2.12.2 **Troponin**

Troponin I (also referred to as troponin in this protocol) will be measured by central laboratory in this study. The central laboratory troponin samples may be batched for

analysis and may be assayed several weeks or months after collection. Therefore, the results of the central laboratory troponin analysis will not be routinely provided to the investigator.

At any time during a subject's study participation when local troponin I or T are drawn to evaluate suspected myocardial ischemia or infarction, additional samples for cardiac troponin and/or CK-MB analysis by the central laboratory must be collected. A sample for PK analysis should be collected as well unless it has been more than 5 days since the last administration of IP.

The cardiac troponin assay selected for Study 20120227 is the Siemens ADVIA Centaur Ultra Troponin I, an assay designated as "guideline acceptable" per the European Society of Cardiology/American College of Cardiology Foundation/American Heart Association/World Heart Federation (ESC/ACCF/AHA/WHF) Expert Consensus Document on the Universal Definition of Myocardial Infarction ([Apple FS, 2009](#); [Thygesen et al, 2012](#)).

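### SAP 6.2 and Appendix A set baseline by calendar date, not by first dose, so an unscheduled post-dose Day 1 troponin or CK-MB can become the baseline and a post-dose ECG can dilute it

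*SAP*

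**What the plan says.** SAP 6.1 defines Study Day 1 as a date: "The date of the first investigational product (IP) administration or the date of enrollment" (the latter for subjects never dosed). SAP 6.2 then gives two baseline rules, both tied to that date:

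- **ECG:** "the baseline value is defined as the mean over all non-missing triplicate averages of 3 (or all available) readings from each set of triplicate", restricted to sets "taken prior to or on Study Day 1".
- **All other variables:** "the baseline value is defined as the last non-missing value collected prior to or on Study Day 1".

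In SAP Appendix A, the BL/Day 1 row covers study day ≤ 1 for every type of assessment. Where an interval holds several records, Appendix A makes two exceptions to its closest-record rule. Vital signs use the latest reading before the first dose on that day. Troponin, CK-MB and creatine kinase use the worst value in the interval.

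The protocol works relative to the dose. Section 6.2.1.1 says "Administration of IP will start with the morning dose on day 1", and also "Baseline procedures must be completed before initiation of IP and can be performed on the same day". In Table 2, footnote c ("Predose in the morning, at study site") is attached to the Day 1 vital signs, ECG, troponin I/CK-MB and NT-proBNP. Unscheduled sampling has no such condition: whenever local troponin is drawn for suspected ischemia or infarction, "additional samples for cardiac troponin and/or CK-MB analysis by the central laboratory must be collected" (section 7.2.12.2). Section 6.2.1.2 adds that serial central troponin I and/or CK-MB samples and serial 12-lead ECGs should be collected when there are signs or symptoms of ischemia.

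**The concern.** Because dosing starts in the morning, the rest of Day 1 is post-dose, yet every Day 1 record meets the SAP's baseline rule. The protocol itself creates the route to such records, through the central samples and ECGs it calls for when ischemia is suspected. A troponin or CK-MB taken for that reason on the afternoon of Day 1 could be stored as the subject's baseline. It would then be missing from the post-baseline data, and every later change for that subject would be measured from the wrong starting point.

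Safety and tolerability form a primary objective. Arms have about 20 subjects and the analyses are descriptive, so one misclassified subject is 1/20 = 5% of an arm in a shift table.

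**Working it through.** The plan states no figure that depends on the baseline rule, so there is nothing to reproduce. The check follows a post-dose Day 1 record through SAP 6.1, 6.2, 10.8 and Appendix A. All subject values below are assumed, for illustration.

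**1. Scheduled records.** Footnote c and protocol 6.2.1.1 place these before the first dose. They give a correct baseline under the current text.

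**2. Troponin and CK-MB, unscheduled post-dose on Day 1.** Table 2 has one scheduled troponin/CK-MB sample up to and including Day 1. With that sample alone, the last and the worst value coincide; they can part once an extra sample exists.

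- Assume predose 0.02, Day 1 post-dose 0.05 and week 2 0.05 ng/mL.
- Change at week 2 under SAP 6.2: 0.05 − 0.05 = 0.00. With a predose baseline: 0.05 − 0.02 = +0.03.
- Keep week 2 at 0.05 and let the Day 1 post-dose value range from 0.03 to 0.10. The 6.2 change then runs from 0.05 − 0.03 = +0.02 to 0.05 − 0.10 = −0.05, against +0.03 throughout with a predose baseline.
- Status under SAP 10.8.2: 0.02 is detected (0.016–0.04) and 0.05 is elevated (> 0.04). The move from detected to elevated is recorded as elevated at baseline and elevated afterwards, so the shift disappears from the table of baseline against worst post-baseline status.
- Conflict between the rules: with two post-dose Day 1 samples, 0.10 then 0.05, SAP 6.2 takes 0.05 (last) and Appendix A takes 0.10 (worst). The week 2 change is then 0.00 or −0.05, depending on which rule the programmer follows; the predose answer is still +0.03.

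**3. ECG, unscheduled post-dose on Day 1.** The baseline is a mean of triplicate averages. With k predose and m post-dose sets, the share of a first-dose shift absorbed into baseline is m/(k + m). Screening and Day 1 predose ECGs are both scheduled, so k = 2.

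- m = 1: 1/3 absorbed. m = 2: 2/4 = 1/2 absorbed.
- Reported change for a shift D that persists at later visits, with m = 1: D − D/3.
- D = 45 msec: 45 − 15 = 30, which moves the subject from the > 30–60 category of SAP 10.8.4 to ≤ 30.
- D = 75 msec: 75 − 25 = 50, which moves the subject from > 60 to > 30–60.
- SAP 10.8.4 counts unscheduled ECGs towards the maximum change and the maximum post-baseline value, but a Day 1 ECG already sits in the baseline interval.

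**4. Vital signs, post-dose on Day 1.** The Appendix A exception selects the latest reading before the first dose that day, so none of a first-dose shift enters baseline. SAP 6.2 does not refer to this exception; read alone, it would admit the post-dose reading in full.

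**5. Records dated Day 2 or later.** For troponin, CK-MB and ECG these fall in the week 2 window (> 1 to ≤ 21). There the worst troponin or CK-MB value is used, and unscheduled ECGs count towards the QTc maxima.

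**6. Events.** Under Appendix B, an adverse event with onset on the first dosing date and flagged as not starting before the first dose is treatment-emergent. SAP 10.7 counts adjudicated events from the first dose date.

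**The case against.** The strongest reply is that the plan is largely safe in practice. Scheduled baseline data are predose. The records at issue arise only if ischemia is suspected within hours of the first dose, or if a sample is mistimed. A suspected ischemic event would still appear as a treatment-emergent adverse event and go to adjudication, and the DMC reviews unblinded data about monthly. Serial sampling that runs past midnight yields post-baseline records. No hypothesis is tested.

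All of this stands, and it limits the point to a few subjects' laboratory and ECG summaries. It does not remove the defect: for a troponin or CK-MB series dated entirely on Day 1, the stated rules can select a post-dose baseline and leave no record of that episode after baseline.

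A reader might infer more: that a post-dose troponin, ECG or vital sign each replaces the baseline, so that a first-dose effect is hidden. The documents do not support that. ECG has its own averaging rule and is only diluted, vital signs have a dose-relative exception, and the event data are intact. Nor is the stored troponin necessarily the peak: SAP 6.2 takes the last value, and only Appendix A takes the worst.

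**Conclusion.** The point holds as a minor but real error of definition. SAP 6.2 and the baseline row of Appendix A omit the before-dosing condition that the protocol imposes.

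- **Troponin and CK-MB:** a post-dose Day 1 value can be taken whole as baseline, under two rules that disagree, and is then left out of the worst post-baseline table.
- **ECG:** about one third of a shift is absorbed with two predose sets and one post-dose set, and one half with two post-dose sets.
- **Vital signs:** no loss if the Appendix A exception governs; only a cross-reference is missing.
- **Adverse events and adjudicated events:** not affected.

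The number of subjects cannot be derived from the documents; that it is small is an assumption. The ECG figures also assume that the predose sets agree, that the shift persists, and that the unscheduled tracing reaches the analysis data as its own set.

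**What to change.** 1. In SAP 6.2 and the BL row of Appendix A, define baseline as the last non-missing value collected before the date and time of first dosing; for ECG, as the mean of the triplicate averages collected before it.
2. Treat scheduled Day 1 samples without a recorded time as predose, and say how an unscheduled Day 1 record without a time is handled.
3. Assign post-dose Day 1 records to the first post-baseline window, and include them in the worst and maximum post-baseline summaries of SAP 10.8.2 and 10.8.4.
4. State that the worst-value rule for troponin, CK-MB and creatine kinase does not apply to baseline.
5. Cross-reference the Appendix A vital-sign exception in SAP 6.2.

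The cost is a few sentences and a date-time comparison in programming. Dose times are recorded on the eCRF (protocol 6.2.1.1). Sample times are recorded in site source documents (protocol 7.2.12), so the team should confirm that they also reach the analysis data. No new data collection or protocol amendment appears necessary.

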6.3 PK Related Definitions

C_{max}

Observed maximum concentration in Week 8.

C_{2h}

Observed concentration at 2 hours after morning IP administration in Week 16.

t_{max}

Observed time to achieve C_{max} .

$C_{predose}$

Observed concentration at the end of 12-hour treatment interval.

AUC_{8h}

Area under the plasma concentration-time curve estimated for 8 hours in week 8.

$C_{max}/C_{predose}$ ratio

Estimated with C_{max} and $C_{predose}$ observed in week 8.

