2.2.2.1 Studies in Healthy Volunteers

CY 1111, a first-in-human clinical study with omecamtiv mecarbil, was a randomized, double-blind, placebo-controlled, 4-period crossover, dose escalation study designed to evaluate the safety, tolerability, and PK/PD profile of omecamtiv mecarbil administered IV to healthy male volunteers ([Teerlink et al, 2011](#)). This study included a total of 33 subjects who received infusions of omecamtiv mecarbil at doses ranging from 0.005 mg/kg/hr to 1.0 mg/kg/hr for up to 6 hours. The exposures of omecamtiv mecarbil, as measured by area under the curve (AUC) and maximum observed concentration (C_{max}), were approximately dose proportional, with an AUC of 159 (57 standard deviation) ng•hr/mL for treatment administered at an infusion rate of 0.005 mg/hr/kg and 30400 ng•hr/mL when administered at a rate of 1 mg/hr/kg; corresponding C_{max} values for those administration rates were 8.70 (2.20) ng/mL and 1340 ng/mL. The mean clearance ranged from 125 to 207 mL/hr/kg and the mean half life ranged from 17.1 to 23.2 hours and increased slightly with increasing doses. The mean steady state distribution volume was dose independent and ranged from 3.6 to 5.2 L/kg. At the dose of 0.5 mg/kg/hr over 6 hours, the mean (standard deviation [SD]) C_{max} was 905 (183) ng/mL. Across the dosing levels evaluated in CY 1111, omecamtiv mecarbil infusions demonstrated generally linear PK with dose-proportional increases in C_{max} . Concentration-dependent PD effects on cardiac function as measured by echocardiography were observed. These PD effects included statistically significant placebo corrected increases from baseline in SET, Doppler-derived stroke volume, left ventricular ejection fraction (LVEF), and fractional shortening.

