CY 1013 was an open-label, parallel group study in healthy male volunteers designed to evaluate the contribution of cytochrome P450 enzymes CYP3A4 and CYP2D6 to the elimination of omecamtiv mecarbil. Healthy volunteer subjects who were either extensive metabolizers (EMs) or poor metabolizers (PMs) with respect to their defined CYP2D6 genotype received oral omecamtiv mecarbil alone and in combination with ketoconazole or diltiazem. Ketoconazole (a potent inhibitor of CYP3A4) caused approximately 51% and 31% increases in the mean AUC of omecamtiv mecarbil in EM and PM subjects, respectively; 1 PM subject had a decrease in omecamtiv mecarbil AUC when given in combination with ketoconazole which contributed to the observed

differences between these 2 groups. In the presence and absence of diltiazem (a moderate inhibitor of CYP3A4), the AUC of omecamtiv mecarbil was similar. CYP3A4 inhibition had little impact on C_{max} and time to C_{max} . When omecamtiv mecarbil was administered alone, the mean AUC was approximately 37% higher in PM subjects (990 ng•hr/mL, n = 8) than in EM subjects (720 ng•hr/mL, n = 8). These results indicate minor involvement of CYP3A4 and CYP2D6 in the metabolism of omecamtiv mecarbil.

Studies CY 1011, CY 1015, and CY 1016 were designed to evaluate the PK parameters of oral preparations of omecamtiv mecarbil. The studies enrolled a total of 44 males and 20 females. Maximal duration of exposure was 10 days and maximal dose was 30 mg 3 times a day for 7 days. Results from the studies demonstrated very high oral bioavailability for omecamtiv mecarbil approaching 100% under all conditions studied; food appeared to reduce the rate but not the extent of absorption. Omecamtiv mecarbil was well tolerated with no treatment-related serious adverse events in these trials.

In Study 20090727, which compared five modified-release (MR) formulations to the IR formulation, the mean bioavailability of the MR formulations was ~80% with MR-F1, MR-F2 and SCT-F2 and C_{max} was reduced by ~70%. Food had a minimal effect on the PK of the oral MR and immediate release (IR) formulations but reduced inter-subject variability.

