Table of Abbreviations

Abbreviation or Term	Definition/Explanation
ACE	angiotensin-converting enzyme
AE	adverse event
ALP	alkaline phosphatase
ALT	alanine aminotransferase
ARB	angiotensin receptor blocker
AST	aspartate aminotransferase
AUC	area under the curve
AUC ₁₂	area under the concentration-time curve for a 12 hour-dosing interval
AUC _t	area under the concentration-time curve calculated by linear trapezoidal method
ANCOVA	analysis of covariance
BID	twice daily
BMI	body mass index
BNP	brain-type natriuretic peptide
Bpm	beats per minute
C _{2h}	observed plasma concentration 2 hours after morning investigation product administration
CAS	completer analysis set
CDM	clinical data management
CEC	clinical events committee
CHF	chronic heart failure
CI	confidence interval
CK-MB	creatinine kinase MB fraction
C _{max}	maximum observed plasma concentration
CPMS	Clinical Pharmacology, Modeling and Simulation
C _{predose}	plasma concentration prior to the investigational product administration
CSR	clinical study report
CTCAE	common terminology criteria for adverse events; common toxicity criteria for adverse events
DLRM	dose level review meeting
DMC	data monitoring committee
DQR	data quality review
ECG	electrocardiogram
eCRF	electronic case report form

Abbreviation or Term	Definition/Explanation
eGFR	estimated glomerular filtration rate; eGFR will be calculated by the central laboratory and provided to the investigator
EOI	events of interest
EOS	end of study (for individual subject)
E-R	exposure-response
FAS	full analysis set
HF	heart failure
HR	heart rate
IBG	independent biostatistical group
IP	investigational product
IPD	important protocol deviation
IVRS	interactive voice response system
LLOQ	lower limit of quantification
LVEDD	left ventricular end-diastolic diameter
LVEDV	left ventricular end-diastolic volume
LVEF	left ventricular ejection fraction
LVESD	left ventricular end-systolic diameter
LVESV	left ventricular end-systolic volume
LVFS	left ventricular fractional shortening
MedDRA	medical dictionary for regulatory activities
MI	myocardial infarction
MR	modified-release
NYHA	New York heart association
NT-proBNP	n-terminal proBNP (brain natriuretic peptide)
PK/PD	pharmacokinetic/pharmacodynamic
PKAS	pharmacokinetic analysis set
PKS	Pharsight Knowledgebase Server
PR interval	PR interval is measured from the beginning of the P wave to the beginning of the QRS complex in the heart's electrical cycle as measured by ECG
PT	prothrombin time

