QRS complex	interval between the Q wave and the S wave in the heart's electrical cycle as measured by ECG; represents the time it takes for the depolarization of the ventricles
QT interval	measure of the time between the start of the Q wave and the end of the T wave in the heart's electrical cycle as measured by ECG
QTcB interval	QT interval corrected for heart rate using Bazett's formula

Abbreviation or Term	Definition/Explanation
QTcF interval	QT interval corrected for heart rate using Fridericia's formula
RR interval	interval between successive Rs where R is a point corresponding to the peak of the QRS complex as measured by ECG
SAE	serious adverse event
SAP	statistical analysis plan
SD	standard deviation
SET	systolic ejection time
SV	stroke volume
$t_{1/2}$	terminal half-life
t_{\max}	time to C_{\max}
ULN	upper limit of normal
URL	upper reference limit

Also refer to the protocol for more abbreviations on clinical terms.

1. Introduction

The purpose of this Statistical Analysis Plan (SAP) is to provide details of the statistical analyses that have been outlined within the protocol for AMG 423 (Omeamtiv Mecarbil) Study 20120227, dated 23 October 2015. The scope of this plan includes the final analyses that are planned and will be executed by the Biostatistics department. The pharmacokinetics (PK) analysis will be performed by Department of Clinical Pharmacology, Modeling and Simulation (CPMS).

2. Objectives

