4.1 Study Endpoints

4.1.1 Primary Endpoints

- Concentrations prior to administration (C_{predose}) of omecamtiv mecarbil at weeks 2, 4, 12, and 16, and area under the curve (AUC) at week 8

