10.5 Analyses of Primary Endpoints

The primary endpoints are omecamtiv mecarbil PK parameters $C_{predose}$ and AUC, collected in the study ([Section 4.1.1](#)).

All data for PK analyses will be extracted from a secure folder and mapped via a clinical connector into the Pharsight Knowledgebase Server (PKS) system (Pharsight Corporation, St. Louis, MO).

Omecamtiv mecarbil plasma concentration-time data will be analyzed by noncompartmental methods using Phoenix WinNonlin (Pharsight Corporation, St. Louis, MO) and will be stored in the validated PKS system. Concentration values less than or

equal to the lower limit of quantification (LLOQ, 1 ng/mL) will be set to zero in the analysis dataset. In the PK data analysis, LLOQ value (zero) will be excluded.

Actual doses administered and actual or nominal sampling times post drug administration will be used in the noncompartmental analysis. Nominal times will be used for presenting data in graphs and tables. All pharmacokinetic parameters and summary statistics will be presented to 3 significant digits.

Summary statistics of PK parameters will include mean, standard deviation and CV%; median and range; geometric mean and CV% of geometric mean. Each pharmacokinetic parameter will be summarized by dose level and sampling time.

In the pharmacokinetic analysis, the following parameters will be estimated:

- Observed maximum concentration (C_{\max})
- Observed time to achieve C_{\max} (t_{\max})
- Observed concentration prior to next dose (C_{predose})
- Area under the plasma concentration-time curve (AUC_t) calculated by linear trapezoidal method
- Ratio of $C_{\max} / C_{\text{predose}}$

Individual concentration-time data will be tabulated and presented graphically. Mean concentration-time profiles for each dose will be provided.

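### The primary week-8 AUC is in effect AUC0-8 under 12-hourly dosing; AUC0-12 could be reported beside it from samples already taken

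*SAP*

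**What the plan says.** SAP 4.1.1 gives the primary endpoint as predose concentrations at weeks 2, 4, 12 and 16 and "area under the curve (AUC) at week 8". Protocol 10.1.1.1 agrees. Neither states an interval at that point.

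Three AUC labels appear elsewhere in the SAP:
- Section 6.3 defines AUC8h: "Area under the plasma concentration-time curve estimated for 8 hours in week 8".
- Section 10.5, the analysis of the primary endpoints, lists "Area under the plasma concentration-time curve (AUC_t) calculated by linear trapezoidal method", with t not stated.
- The table of abbreviations has AUC12, the "area under the concentration-time curve for a 12 hour-dosing interval". No endpoint, definition or method uses it.

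Protocol Table 2, footnote j, sets the week-8 samples at predose, 2, 4, 6 and 8 h. Protocol 6.2.1.1 sets dosing every 12 h, give or take 3 h. SAP 6.3 describes Cpredose as the concentration at the end of the 12-hour interval, but no rule uses it to close the curve at 12 h.

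**The concern.** Read together, these sections lead to AUC0-8. Under 12-hourly dosing that omits the last third of the interval. The level of exposure is itself the result in an estimation-only trial, and the dose rationale in Protocol 2.3 presents exposure as AUCss (Table 1). A reader who sets the reported AUC beside Table 1 would see lower exposure than simulated for a reason that has nothing to do with the subjects. Three labels for one quantity make that easier to miss.

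**Working it through.** **The plan's own figure.** The precision table (Protocol Table 4, SAP 3.2) reproduces with half width = 1.96 × SD/√19: SD 40 gives 17.99 and SD 90 gives 40.47, against 18.0 and 40.5. For a given SD it does not depend on the AUC interval, so it does not settle the question.

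**A bound that needs no absorption model.** In any subject AUC0-8 ≤ 8 × Cmax, so the same holds for means. From Table 1:

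| Row | Cmax,ss | AUCss | 8 × Cmax,ss | 8 × Cmax,ss / AUCss |
|---|---|---|---|---|
| Japanese 25 mg | 277 | 2759 | 2216 | 0.803 |
| Japanese 37.5 mg | 461 | 4613 | 3688 | 0.799 |
| Japanese 50 mg | 614 | 6143 | 4912 | 0.800 |
| Non-Japanese 25 mg | 211 | 2115 | 1688 | 0.798 |
| Non-Japanese 37.5 mg | 351 | 3521 | 2808 | 0.798 |
| Non-Japanese 50 mg | 469 | 4707 | 3752 | 0.797 |

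AUCss exceeds 8 × Cmax,ss in every row, so it cannot be an 8-hour AUC. If it covers 12 h, AUC0-8 leaves out at least about 20%.

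**Is 12 h reasonable for Table 1?** The alternative is 24 h.
- *Shape.* Over 24 h, Cavg/Cmax would be (2759/24)/277 = 0.415, and up to 0.418 in the other rows. With instantaneous absorption the lowest possible ratio is (1 − e^(−12k))/(12k). A value near 0.415 needs a half-life of about 3.9 h. Protocol 2.2.2.1 reports that "The mean clearance ranged from 125 to 207 mL/hr/kg and the mean half life ranged from 17.1 to 23.2 hours"; at 17.1 h the lowest ratio is 0.792.
- *Mass balance.* Take bioavailability 0.8, the highest clearance of 207 mL/hr/kg and 58 kg. The 24-h AUC on 25 mg BID is then at least 0.8 × 50,000,000 ng / (207 × 58 mL/h) = 3332, above 2759. One 25 mg dose gives 1666 (bioavailability 0.8, clearance 207) to 3448 (bioavailability 1.0, clearance 125), which brackets 2759.

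These inputs come from IV dosing in healthy men and a mean bioavailability for modified-release tablets, so 12 h remains an inference.

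**Model estimates.** One compartment, steady state, τ = 12 h:

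C(t) ∝ ka/(ka − k) × [e^(−kt)/(1 − e^(−12k)) − e^(−ka·t)/(1 − e^(−12ka))]

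The absorption rate ka is an assumption.

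| Model set | True AUC0-8 / AUC0-12 | Left out | 0-12 h trapezoid with C12 = C0, recovery |
|---|---|---|---|
| Matched to Table 1 (Cavg/Cmax 0.833): half-life 4.1-21 h, ka 0.2-18.8/h | 0.709-0.723 | 28-29% | 0.969-0.989 |
| Protocol half-lives 17.1-23.2 h, ka 0.15-1.5/h | 0.673-0.711 | 29-33% | 0.983-0.998 |

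Neither set fits everything. The first needs either half-lives shorter than the protocol's or very fast absorption for a modified-release tablet. The second gives Cavg/Cmax of 0.85-0.97, above Table 1. The span of both is 28-33%. For the Japanese 25 mg mean that is 2759 × 0.67 = 1849 to 2759 × 0.72 = 1986, with a ceiling of 2216.

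**The 12-h value.** By linear trapezoid, AUC0-8 = C0 + 2C2 + 2C4 + 2C6 + C8. The last segment adds 4 × (C8 + C12)/2 = 2(C8 + C12), with C12 = C0 at steady state. Away from steady state, the matched models recover these shares of the actual next 12 h: 96-101% when the previous dose was 9 or 15 h earlier, 88-94% after a missed evening dose, 94-96% for a first 1.5-fold dose and 92-94% for a first doubled dose.

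**The case against.** A reader might infer that the primary AUC has no defined interval. The documents do not support that. SAP 6.3 gives 8 hours, SAP 10.5 places AUC_t under the primary analysis, and sampling stops at 8 h. The interval can be found; what remains is inconsistent labelling and an unused abbreviation.

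It is also fair to say that AUC0-8 is fully observed, whereas AUC0-12 fills the last third of the interval with an imputed end point. No hypothesis is tested and no comparison with Table 1 is planned. The 8-h share is nearly constant across dose rows, so comparisons between arms hardly move. All of this stands. It limits the consequence to the reported level of exposure, and it is why AUC0-8 should be kept.

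A reader might further infer that up-titration at the week-8 visit counts against AUC0-8 in particular. It does not, because it affects both measures. If the first higher dose is the one taken at that visit, which the documents do not state, the matched models put AUC0-8 at 0.65-0.86 and AUC0-12 at 0.61-0.84 of the steady-state value at the new dose, while SAP 10.5 says "Each pharmacokinetic parameter will be summarized by dose level and sampling time". That is a reason to restrict AUC0-12, not evidence against AUC0-8.

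Finally, SAP section 1 assigns the PK analysis to a separate department, which may hold a fuller specification. These documents do not show one.

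**Conclusion.** The point holds as a cheap improvement. On the only reading that the SAP supports, the primary AUC is AUC0-8, which is not exposure per 12-h dosing interval. The shortfall is at least about 20% if Table 1 covers 12 h, and about 28-33% under one-compartment models with an assumed absorption rate. That 8 h is impossible for Table 1 is arithmetic; that it is 12 h is inferred. A reader might take this to mean that the PK data are unusable or the dose comparisons biased. Neither follows: AUC0-8 is a valid partial measure, and the effect is on the level reported, not on contrasts between arms.

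**What to change.** 1. Use one AUC label, with its interval, in SAP 4.1.1, 6.3 and 10.5, and either use or delete AUC12.
2. Keep the observed week-8 AUC0-8. Beside it, report week-8 AUC0-12 by linear trapezoid on 0, 2, 4, 6, 8 and 12 h, with C12 set to the week-8 predose concentration, in line with the SAP's own description of Cpredose.
3. Derive AUC0-12 only for subjects whose dose has not changed since the week-4 visit (including at the week-8 visit) and whose diary shows that the preceding evening dose was taken. List the others separately. The diary in Protocol 7.2.5 already records the date and time of each dose taken away from the site.

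The cost is SAP wording and one derived time point, with no new sample. The downside is one imputed value that relies on steady state; modelled recovery is then about 97-99.8% of AUC0-12.
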